5.6 Follow-Up After Subject Discontinuation of Study Drug or from Study

Discontinuation of Study Drug and Continuation of Study Participation

To minimize missing data for efficacy and safety assessments, subjects who prematurely discontinue study drug treatment should be encouraged to continue to be followed for all regularly scheduled visits (except for visits that are intended only for study drug administration [Weeks 6, 10, 14, 18, 22, 26, 30, 34, 38, 42, 46, and 50]), unless the subject has decided to discontinue the study participation entirely (withdrawal of informed consent). At the visits after study drug discontinuation, subjects should adhere to all study procedures except for dispensing of study drug and accountability, dosing diaries, and PK (conjugated ADC, total antibody, free A-1677770 assays) and immunogenicity (ADA assays) sample collection. Subjects should be advised on the continued scientific importance of their data even if they discontinue treatment with study drug early. Following discontinuation of study drug, the subject should be treated in accordance with the investigator's best clinical judgment irrespective of whether the subject decides to continue participation in the study.

If a subject prematurely discontinues study drug, the procedures outlined for the Premature Discontinuation Visit should be completed as soon as possible, preferably within 2 weeks, and preferably prior to initiation of another therapy.

In addition, a 30-day Follow-up Phone Call and 70-Day Follow-up Visit after the last dose of study drug is required to ensure all treatment-emergent AEs/SAE have been resolved. All attempts must be made to determine the date of the last study drug dose and the primary reason for discontinuation of study drug or study participation. This information will be recorded on the appropriate eCRF page. This Follow-up

Phone Call is not applicable for subjects who discontinued study drug prematurely and continued study participation with completion of at least 1 study visit that was at least 30 days after the last dose of study drug. This visit is not applicable for subjects who discontinued study drug prematurely and continued study participation with completion of at least 1 study visit that was at least 70 days after the last dose of study drug.

Premature Discontinuation of Study (Withdrawal of Informed Consent)

If a subject prematurely discontinues study participation (withdrawal of informed consent), the procedures outlined for the Premature Discontinuation visit should be completed as soon as possible, preferably within 2 weeks, and preferably prior to initiation of another therapy.

For subjects to be considered lost to follow-up, reasonable attempts must be made to obtain information on the subject's final status. At a minimum, 2 telephone calls must be made, and 1 certified letter must be sent and documented in the subject's source documentation.

If a subject withdraws from study follow-up or withdraws permission for the collection of their personal data, the study staff may still use available public records to obtain information about survival status only, as appropriate per local regulations.

In the event a subject withdraws consent from the clinical study, optional biomarker research will continue unless the subject explicitly requests analysis to be stopped. When AbbVie is informed the subject has withdrawn and no longer wishes biomarker samples research to continue, samples will not be analyzed and no new biomarker analysis data will be collected for the withdrawn subject or added to the existing data or database(s). A subject may withdraw consent for optional biomarker research at any time and remain in the clinical study. Data generated from clinical study and/or optional biomarker research, before subject withdrawal of consent, will remain part of the study results.

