Urine pregnancy test (females of childbearing potential)		✓				✓		✓		✓			✓		✓		✓			✓		✓
																						
Serum pregnancy test (females of childbearing potential); FSH if applicable	✓																					
High-sensitivity C-reactive protein (hsCRP)	✓	✓				✓		✓		✓			✓		✓		✓		✓	✓	✓	
Hematology (*Weeks 28, 36, 44, and 52)	✓	✓				✓		✓		✓			✓		✓		✓		✓*		✓	✓
Glycated hemoglobin (HbA1c) (*Weeks 36 and 52)	✓									✓							✓		✓*			✓
Clinical chemistry (*Weeks 28, 36, 44, and 52)	✓	✓				✓		✓		✓			✓		✓		✓		✓*		✓	✓
Lipid profile (*Weeks 36 and 52)		✓								✓							✓		✓*			
Urinalysis	✓	✓				✓		✓		✓			✓		✓		✓		✓		✓	
Thyroid-stimulating hormone (TSH)	✓																					
Tuberculosis (TB) Test (QuantIFERON TB Gold test and/or local purified protein derivative [tuberculin] skin test)	✓																					
Human immunodeficiency virus (HIV); hepatitis B virus (HBV) and hepatitis C virus (HCV) (Note: HBV	✓																					

Activity	Screening	Baseline	Optional PK	Wk 1	Wk 2	Wk 4	Wk 6	Wk 8	Wk 10	Wk 12	Optional PK	Wk 14	Wk 16	Wk 18	Wk 20	Wk 22	Wk 24	Wks 26 – 52 ^a	Unscheduled for flare evaluation ^b	Premature Discontinuation	30-Day Follow-up Phone Call	70-Day Follow-up Visit
	Day -35 to Day 1	Day 1	Days 3, 4	Day 8	Day 15	Day 29	Day 43	Day 57	Day 71	Day 85	Days 87, 88, 92	Day 99	Day 113	Day 127	Day 141	Day 155	Day 169	EOW Visits				
DNA PCR every 12 weeks where required)																						
Rheumatoid factor, anti-citrullinated protein (anti-CCP) antibody	✓																					
25-hydroxyvitamin D		✓																				
Beta-D-glucan (Japan only)	✓																					
Blood samples for conjugated antibody-drug-conjugate (ADC) (serum), total antibody (serum), free A-167770 (plasma) assays (predose on dosing days)		✓		✓	✓	✓		✓		✓		✓		✓		✓		✓		✓		✓
Blood samples for anti-drug antibody (ADA) assays (including ADA titer and neutralizing antibody [nAb]) (predose on dosing days)		✓			✓			✓		✓		✓		✓		✓		✓		✓		✓
Optional pharmacokinetic (PK) assessments			✓								✓	✓										

Activity	Screening	Baseline	Optional PK	Wk 1	Wk 2	Wk 4	Wk 6	Wk 8	Wk 10	Wk 12	Optional PK	Wk 14	Wk 16	Wk 18	Wk 20	Wk 22	Wk 24	Wks 26 – 52 ^a	Unscheduled for flare evaluation ^b	Premature Discontinuation	30-Day Follow-up Phone Call	70-Day Follow-up Visit
	Day -35 to Day 1	Day 1	Days 3, 4	Day 8	Day 15	Day 29	Day 43	Day 57	Day 71	Day 85	Days 87, 88, 92	Day 99	Day 113	Day 127	Day 141	Day 155	Day 169	EOW Visits				

Rx TREATMENT

Randomization/drug assignment		✓																				

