Rationale: To collect additional data on subjects Baseline status which may affect bone mineral density.
- Protocol [Appendix F](#), Activity Schedule; Operations Manual Section 2.4, Individual Post-Treatment Period Visit Activities: Added PK and immunogenicity sample collection at the 70-day Follow-Up Visit.

Rationale: To ensure drug washout and assess immunogenicity during drug washout.
- Operations Manual, Section 1, Contacts: Updated Clinical Lab and Biomarker Sample Storage contact information.

Rationale: Administrative change.
- Operations Manual, Section 2.1, Individual Treatment Period Visit Activities: All individual study day headers were updated to include an additional column.

Rationale: Added for alignment with the 30-day phone call column in the Study Activity Table.
- Operations Manual, Section 2.1, Individual Treatment Period Visit Activities: For screening visit, changed reference for Section 3.6 to 3.5, describing chest x-ray.

Rationale: To correct typographical error.
- Operations Manual, Section 2.2 Premature Discontinuation Visit, Footnote b: Footnote was removed.

Rationale: Footnote was not applicable to the premature discontinuation visit anymore since subjects no longer wear the device continuously.
- Operations Manual Section 3.2, Rescreening: Added additional opportunity for rescreening of subjects with the AbbVie Therapeutic Area Medical Director/Scientific Director approval.

Rationale: To allow subjects who have already been screened twice the opportunity to rescreen on a case-by-case basis, if appropriate.
- Operations Manual Section 3.2, Rescreening: Added FSH to the list of testing not required to be repeated if rescreening a subject within 14 days from the sample collection date of the previous screen.

Rationale: To reduce unnecessary procedures, as FSH would not be expected to change significantly in 14 days.
- Operations Manual Section 3.6, Dual-Energy X-Ray Absorptiometry (DXA) Scan: Added collection of Z-score for evaluation of bone mineral density and instruction that measurements should be obtained from the distal forearm if the spine nor either hip are able to be scanned or

interpreted. Added a Central Imaging Core Lab for central independent review of DXA data and modified guidance for image acquisition.

Rationale: To improve the robustness and interpretability of the DXA data collected.

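### Subjects who stop study drug by about Week 42 and stay in follow-up lose the washout PK and ADA sample planned for 70 days after last dose

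*Protocol*

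**What the plan says.** Three parts of the protocol bear on this.

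- **Sampling after stopping drug (Protocol 5.6).** A subject who stops early but stays in the study attends the regular visits, other than those held only for dosing, with everything done as scheduled "except for dispensing of study drug and accountability, dosing diaries, and PK (conjugated ADC, total antibody, free A-1677770 assays) and immunogenicity (ADA assays) sample collection". At the time of stopping, "the procedures outlined for the Premature Discontinuation Visit should be completed as soon as possible, preferably within 2 weeks".
- **The 70-Day Follow-up Visit (Protocol 5.6).** By default a "70-Day Follow-up Visit after the last dose of study drug is required to ensure all treatment-emergent AEs/SAE have been resolved". The waiver then reads: "This visit is not applicable for subjects who discontinued study drug prematurely and continued study participation with completion of at least 1 study visit", where that visit must fall 70 or more days after last dose.
- **What the 70-Day Visit collects (Appendices F and G).** Appendix F has a row for ADA samples and one for PK samples. The extracted table is broken, but the last two ticks in the ADA row read as the Premature Discontinuation Visit and the 70-Day Follow-up Visit. Appendix G confirms that PK and immunogenicity sampling was added to the 70-Day Visit and gives the reason: "To ensure drug washout and assess immunogenicity during drug washout".

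Immunogenicity is part of the secondary objective (Protocol 3.1). Protocol 7.6 plans descriptive summaries of ADA and neutralising-antibody incidence and of ADA titer by group. SAP 3.5 leaves the analysis to a separate plan.

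**The concern.** The waiver suits the purpose that Section 5.6 gives for the 70-Day Visit, because a later regular visit can check adverse events equally well. It does not suit the second purpose, added with the sampling. The replacing visit falls under the sampling exclusion, and nothing in the supplied text carries the washout sample over to it.

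Completers, whose last dose is at Week 50, keep the 70-Day Visit and its sample. Most subjects who stop early and do as the protocol encourages, by staying in follow-up, do not. The chance to detect ADA off drug therefore depends on whether a subject stopped early and stayed. A missing later sample can lose positives but cannot add any. What is at stake is the completeness of the descriptive ADA data, and whether subjects who stopped early can be compared with completers.

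**Working it through.** No sample-size or power figure is involved, so there is no plan figure to reproduce. The check is visit-calendar arithmetic followed by a residual-drug calculation.

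**1. Which last doses lose the sample?**

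Inputs:
- Dosing is every other week with the final dose at Week 50 (Protocol 5.8). Possible early last doses are therefore Weeks 0, 2, ..., 48, which is 25 slots.
- Regular visits that remain after stopping are Weeks 1, 2, 4, 8, 12, 16, 20, 24, 28, 32, 36, 40, 44, 48 and 52 (Appendix F, less the dosing-only visits listed in Protocol 5.6).

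Rule: the 70-Day Visit is waived if some regular visit V and last dose D satisfy 7 × (V − D) ≥ 70, that is V ≥ D + 10, and the subject completes that visit.

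| Last dose (week) | First regular visit at 70+ days | Days after last dose | 70-Day Visit |
|---|---|---|---|
| 0, 4, 8, ..., 40 (11 slots) | D + 12 | 84 | waived |
| 2, 6, 10, ..., 42 (11 slots) | D + 10 | 70 | waived |
| 44 | none (Week 52 is at 56 days) | – | kept |
| 46 | none (Week 52 is at 42 days) | – | kept |
| 48 | none (Week 52 is at 28 days) | – | kept |

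So 11 + 11 = 22 of 25 slots lose the sample if the visit is attended. Example: a last dose at Week 10 is Day 71 and Week 20 is Day 141; 141 − 71 = 70, so the 70-Day Visit is waived and Week 20 takes no PK or ADA sample.

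This uses nominal days, because visit windows are not in the supplied text. A Week 52 visit held one day early would be 69 days after a Week 42 dose, and the 70-Day Visit would then stay. The boundary is therefore about Week 42.

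**2. Is the Premature Discontinuation sample a washout sample?**

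SAP 10.2.1 equates 70 days with 5 half-lives: 70 / 5 = 14 days. Appendix G says 70 days exceeds five times the upper limit of the mean half-life, so 14 days is an upper figure. Shorter values are shown as assumptions. Fraction remaining = 0.5^(t / half-life).

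| Half-life | 14 days | 28 days | 70 days |
|---|---|---|---|
| 14 days (SAP, upper figure) | 50% | 25% | 3.1% |
| 10 days (assumed) | 38% | 14% | 0.8% |
| 7 days (assumed) | 25% | 6% | 0.1% |

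The two-week preference is not stated to run from the last dose. A subject who stops when the next dose is due, and is seen within two weeks of that, is sampled about 14 to 28 days after last dose. Across the table, 6% to 50% of drug then remains, against 0.1% to 3.1% at 70 days.

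**3. How many subjects?**

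The documents give no rate of stopping drug while staying in the study. If 10% to 25% of the 3 × 40 = 120 active-arm subjects did so (an assumption), that is 12 to 30 subjects, less those whose last dose is at Weeks 44 to 48 or who complete no visit at 70+ days. This counts missing samples, not missed ADA positives.

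**The case against.** The strongest reply is that these subjects are still sampled at the Premature Discontinuation Visit. Routine on-treatment ADA samples are taken predose on dosing days, about two weeks after the previous dose, so the discontinuation sample meets a similar or lower drug level than the samples the study relies on throughout. For a suspected systemic hypersensitivity reaction, Protocol 6.2 also asks for serum within hours, with tests listed in an Operations Manual section that was not supplied. Another Operations Manual section deals with subjects who stop drug and stay, and it too is unseen. ADA is only described, and no planned analysis links it to stopping drug.

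Most of this stands, and it limits what can be concluded. It does not restore a sample off drug, which is what Appendix G says the 70-day sample was added to give.

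A reader might infer three stronger things that the documents do not support:

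- **That subjects who stop early never give the washout sample.** Those with a last dose at Weeks 44 to 48, and those who complete no visit at 70+ days, keep the 70-Day Visit. The exclusion sentence could be read to cover that visit as well, which would conflict with Appendix F and needs reconciling.
- **That everyone else gives it.** For withdrawal of consent, Section 5.6 calls for the Premature Discontinuation procedures and does not mention a 70-day visit.
- **That ADA incidence is under-detected.** The direction is plausible, but the documents give neither the assay's drug tolerance nor the ADA incidence definition and denominator. Neither occurrence nor size can be shown.

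**Conclusion.** The gap is real on the text of Section 5.6. On nominal days, subjects with a last dose up to about Week 42 who stay in the study and complete a visit 70 or more days later give no washout PK or ADA sample. Late-emerging or drug-masked ADA may be missed in them, which makes descriptive ADA incidence less complete and less comparable with completers. The size of any loss cannot be determined from the documents.

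This rests on nominal visit days, on the reading of the broken Appendix F table, and on the unseen Operations Manual not restoring the sample. The severity is low. It is worth correcting because the correction is cheap and a sample not drawn cannot be recovered later.

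**What to change.** In Protocol 5.6, with a matching footnote in Appendix F:

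1. For subjects who stop study drug and remain in the study, collect one PK and one ADA sample at the first attended visit 70 or more days after last dose, when that visit replaces the 70-Day Follow-up Visit.
2. State that the sampling exclusion does not apply to a 70-Day Follow-up Visit that still takes place.

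The cost is two sentences and a footnote, plus one extra blood tube and one assay set per affected subject. Blood is already drawn for hsCRP at these visits, so no visit is added.

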5.7 Disease Activity and Flare Assessment

Assessment of PMR Signs and Symptoms

Subjects will be evaluated for PMR flare by the assessment of PMR signs and symptoms at study visits according to the schedule of assessments and the results entered into the eCRF. PMR signs and symptoms include the presence of any of the following:

- Shoulder and/or hip girdle pain with inflammatory stiffness
- Neck pain with inflammatory stiffness
- New or worsened limited range of motion of hips and/or shoulders

PMR must be confirmed as the cause of the clinical signs and symptoms in each subject by eliminating other causes such as infections, pre-existing medical conditions, and physical activity. Signs and symptoms due to causes other than PMR should not be entered into the eCRF or considered as PMR flare.

Once clinical signs and symptoms of PMR are confirmed for a subject, the investigator should assess if an increase in glucocorticoid dose is required. If an increase in glucocorticoid dose is required, flare is confirmed and the subject should be offered glucocorticoid rescue as described in Section 5.8.

If a subject has a suspected flare at any time during the study, the flare should be confirmed as soon as possible (at a scheduled or unscheduled visit), prior to initiating glucocorticoid rescue treatment. Assessments at a visit where PMR flare is suspected must include assessment of PMR signs and symptoms, hsCRP, ESR, Patient Assessment of Pain Severity NRS, Physician Global Assessment of Disease Activity NRS, MST, EUL, UL-ROM and goniometer measurement for subjects in the Wearable Device Substudy, AE assessment, and concomitant therapy. Additional assessments may be added per the investigator's medical judgement.

Other Disease Activity Assessments

Disease activity will also be assessed through collection of the ESR, PMR-AS components (i.e., hsCRP, Patient Assessment of Pain Severity NRS, Physician Global Assessment of Disease Activity NRS, MST, and EUL), and UL-ROM and goniometer measurement for subjects in the Wearable Device Substudy at study visits as noted in the Activity Schedule (Appendix F) and at any visit where PMR flare is suspected. Further details can be found in the Operations Manual (Appendix H).

5.8 Study Drug

ABBV-154 and Matching Placebo

ABBV-154 and matching placebo will be manufactured and provided by AbbVie (Table 1). Each dose will be administered by a healthcare professional as 3 SC injections (2 prefilled syringes [PFS] with 1.5 mL fill volume and 1 PFS with 0.4 mL fill volume) in the abdomen or thigh. Blinded study drug will be administered EOW at approximately the same time of day, preferably between 7 and 11 a.m., beginning on Day 1 (Baseline Visit). The study drug can be taken with or without food. A 15- to 30-minute observation period is required after each dose. The last dose of ABBV-154/placebo will be given at Week 50.

ABBV-154 and matching placebo syringes will be packaged in cartons with quantities sufficient to accommodate the study design. Each prefilled syringe and carton will be labeled per local requirements and these labels must remain affixed to the syringe and carton. Upon receipt, study drug should be stored as specified on the label (refrigerated at 2 to 8°C) and kept in a secure location. Each kit will contain a unique kit number. This kit number is assigned to a subject via Interactive response technology (IRT) and encodes the appropriate study drug to be dispensed at the subject's corresponding study visit. Study drug must not be dispensed without contacting the IRT system. Site staff will complete all blank spaces on the label before dispensing study drug for the subject. Study drug is for investigational use only and will only be used for the conduct of this study.

Table 1. Investigational Product

Study Drug	Dosage Form	Strength	Route of Administration	Manufacturer
ABBV-154	Solution for Injection/infusion in PFS	40 mg 150 mg	subcutaneous	AbbVie
Placebo for ABBV-154	Solution for Injection/infusion in PFS	Not applicable	subcutaneous	AbbVie

PFS = prefilled syringe

Glucocorticoids

Starting at the Baseline Visit, all subjects will switch from oral glucocorticoids obtained from independent sources to open-label oral prednisone/prednisolone provided by the sponsor at the same dose they were taking just prior to the Baseline Visit, rounded up to the nearest 1 mg to a maximum of 15 mg. At the Baseline Visit (Day 1), the subject may take non-sponsor provided oral glucocorticoid at the required dose prior to randomization so that the subject does not have to delay the usual time of glucocorticoid dosing. If a subject has already taken the glucocorticoid dose at home on the day of the Baseline Visit, dosing should not be repeated with sponsor-provided prednisone/prednisolone. Open-label prednisone/prednisolone will be self-administered orally (PO) once per day (QD) (Table 2). The baseline dosage will be administered QD until the Week 3 visit, at which time tapering will begin as described in Section 6.1 of the Operations Manual (Appendix H). Glucocorticoids should be stored as specified on the label (may differ by manufacturer and local requirements) in a secure location.

Table 2. Non-Investigational Product

Study Drug	Dosage Form	Strength	Route of Administration	Manufacturer
Prednisone/ Prednisolone	Tablets	1 mg, 5 mg, and 10 mg	Oral	Generic ^a

a. Prednisone/prednisolone may be supplied by AbbVie per local requirements.

If a subject or home health nurse (if utilizing home care visits) is unable to come to the study site to pick up their study drug due to COVID-19 or other reasons, a direct-to-patient study drug shipment can be made from the study site to the subject if allowed by local regulations. AbbVie will submit any required notifications to the regulatory authority as applicable.

Subjects will be instructed to return all drug containers (even if empty) to the study site personnel at each study visit; study site personnel will document compliance.

Glucocorticoid Tapering Schedule

Starting at Week 3, prednisone/prednisolone will be tapered to 0 mg prednisone/prednisolone per day according to the schedule in Section 6.1 of the Operations Manual (Appendix H), based on the glucocorticoid dosage at Baseline. The glucocorticoid taper will be completed by Week 24 for all subjects.

Rescue Treatment for PMR Flare

If a subject has a suspected PMR flare at any time during the study, the flare should be confirmed as soon as possible, prior to initiating glucocorticoid rescue treatment. Flare may be confirmed at either a scheduled visit or unscheduled visit. Assessments performed at a visit for suspected flare are listed in Section 5.7 and in the Operations Manual (Appendix H). Additional assessments may be added per the investigator's medical judgement. PMR must be confirmed as the cause of flare by eliminating other causes of the subject's symptoms/signs such as infection or other underlying disease. Once flare is confirmed, glucocorticoid rescue should be administered with the dose and subsequent tapering at the discretion of the investigator, taking into consideration local standard of care, the subject's preflare and/or baseline dose, and not exceeding 15 mg/day. The investigator must record his/her recommendation to increase the prednisone/prednisolone dose due to PMR flare in the eCRF, regardless of whether or not the subject agrees to increase his/her dose. The specific dose of glucocorticoid rescue therapy taken by the subject should be documented in the eCRF.

While receiving open-label rescue treatment with prednisone/prednisolone, the subject should continue in the study and receive blinded study drug (ABBV-154/placebo) unless the subject meets the study drug discontinuation criteria (see Section 5.5).

If a subject remains on prednisone/prednisolone up to the Week 52 visit, the subject will take the last dose of Sponsor-supplied prednisone/prednisolone on the day prior to the Week 52 or on the day of the Week 52 visit and may restart individually-sourced prednisone equivalent on or after the day of the Week 52 visit, under the medical guidance of the investigator.

Addition of immunomodulators other than glucocorticoid rescue, as outlined above, are not permitted for rescue. If the investigator determines it is in the best interest of the subject to start an immunomodulator, the subject must discontinue study drug treatment (ABBV-154/placebo and sponsor-supplied prednisone/prednisolone). Any subsequent medications prescribed by the investigator should be documented on the concomitant medication eCRF.

